## 9.7.3 Methods of Analysis

Descriptive statistics of all endpoints will include specifically but not exclusively, arithmetic mean, standard deviations, medians, minimum, maximum, 25th and 75th percentiles, proportions, frequency counts, and 95% confidence intervals of select point estimates. Figures will be prepared to illustrate the patterns of data over time where appropriate. The number of subjects included in the analysis set will be reported.

## 9.7.3.1 Primary Endpoint

The primary endpoint, the ABR of all types of bleeding episodes, will be calculated for each subject and described for each regimen (on-demand and prophylaxis).

Separate descriptive efficacy analyses of ABR will be provided for each of the following treatment regimens, assuming minimum observed period is satisfied (≥90 days):

- On-demand treatment
- Standard prophylaxis
  - ➤ continuous prophylaxis (≥46 weeks: long-term) 
  - intermittent prophylaxis (≥12 weeks-46 weeks)
  - episodic prophylaxis (<12 weeks)

  - > peri-ITI prophylaxis
- TGA-guided dosing for prophylaxis treatment
- TGA-guided dosing for on-demand treatment

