# 2. LIST OF ABBREVIATIONS AND GLOSSARY

Abbreviation	Definition
ABR	annualized bleed rate
ADL	Activity of Day Living
AE	adverse event
AICC	anti-inhibitor coagulant complex
APCC	activated prothrombin complex concentrates
aPTT	activated partial thromboplastin time
B19V	parvovirus B19
BPA	by-passing agent
BU	Bethesda unit
BW	body weight
CRF	case report form
Chronic pain	continuous and/or intermittent pain, related to the pathophysiology of haemophilia, requiring intervention (pharmacological or non-pharmacological treatment), and in which the cause of pain cannot be readily removed, occurring more than once a week and lasting 3 months or more 
DIC	disseminated intravascular coagulation
EC	ethics committee
ECG	electrocardiogram
eCRF	electronic case report form
ER	emergency room
ETP	endogenous thrombin potential
FEIBA	Factor Eight Inhibitor Bypassing Activity
FEIBA NF	Factor Eight Inhibitor Bypassing Activity Nanofiltered
FVIIa	activated factor VII
FVIII	factor VIII
FIX	factor IX
GPV	Global Pharmacovigilance
HAL	Haemophilia Activities List 
HAV	hepatitis A virus
HBV	hepatitis B virus
HCV	hepatitis C virus
HEV	hepatitis E virus
High responding inhibitors:	inhibitors with peak activity >5 Bethesda Units (BU/ml) at any time associated with anamnesis following replacement of the missing clotting factor 
HIV	human immunodeficiency virus
HJHS	Haemophilia Joint Health Score

Abbreviation	Definition	
HRQoL	Health-Related Quality of Life	
HRUR	health resource used related	
ICF	informed consent form	
IQR	inter quartile range	
ITI	immune tolerance induction	
MAH	marketing authorization holder	
MBR	monthly bleed rate	
MRI	magnetic resonance imaging	
NMC	non-medical complaint	
NRS	numerical rating scale	
NSAE	non-serious adverse event	
On-demand treatment	treatment of acute bleeds with any factor concentrates with the goal to resolve bleeds	
PD	pharmacodynamic(s)	
PedHAL	Pediatric Haemophilia Activity Level	
Prophylaxis	Regular administration of factor concentrates with the goal to prevent bleeds. For analysis purposes, in this protocol, prophylaxis is defined as follows:  • continuous prophylaxis (>46 weeks; long-term)  • intermittent prophylaxis (>12 weeks-46 weeks)  • episodic prophylaxis (≤12 weeks)  • peri-Immune Tolerance Induction (ITI) prophylaxis  For analysis purposes FEIBA prophylaxis is defined as at least three administrations per week 	
QoL	quality of life	
RoM	range of motion	

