#### 9.5 Study Size

As no hypothesis testing or interval estimation will be applied, the sample size for the study is not based on statistical considerations. The sample size of approximately 55 evaluable subjects was selected as a reasonable number for a non-interventional study to recruit in the two-year enrolment period planned for the study.

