## 9.7.1.1 Calculation of Annualized Bleeding Rates (ABR)

The annualized bleeding rates (ABR) will be calculated as follows: (total number of bleeding episodes÷observed treatment period in days) \* 365.25.

The treatment period for emergency surgery will be excluded from the bleed rate calculation.

Bleeding occurring prior to the first prophylactic infusion will not be included for the estimation of bleed rate. The observation period for the on-demand regimen will commence on the day of enrollment (met all inclusion and exclusion criteria); the period for the prophylaxis arm will commence at the first prophylactic infusion once enrolled (met all inclusion and exclusion criteria).

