#### 9.7.1.2 Minimal Observed Treatment Period to Estimate ABR

For enrolled subjects that have met all inclusion and exclusion criteria, subjects who have at least 1 assessment [defined as having a minimum of 3-month (≥90 days) observational period on regimen] but do not complete the full study period of four years, the annualized bleeding rate will be estimated from the interval assessments.

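### The primary-endpoint list gives episodic prophylaxis (<12 weeks) its own ABR analysis but requires at least 90 days on regimen, which no single episodic course can reach; the duration cut-points also conflict

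*Protocol*

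**What the plan says.** Section 9.7.3.1 names the ABR for all bleeds as the primary endpoint, to be calculated per subject and described for on-demand and for prophylaxis. Its next sentence adds separate ABR analyses for a list of regimens, "assuming minimum observed period is satisfied (≥90 days"). Standard prophylaxis is divided into continuous, intermittent, episodic and peri-ITI. The first three are defined by duration, among them "intermittent prophylaxis (≥12 weeks-46 weeks") and "episodic prophylaxis (<12 weeks"); continuous is 46 weeks or more.

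Section 9.7.1.2 says what the minimum is counted on: an assessment is "defined as having a minimum of 3-month (≥90 days) observational period on regimen". Under section 9.7.1.1 the ABR denominator is the observed treatment period in days, and "the period for the prophylaxis arm will commence at the first prophylactic infusion once enrolled".

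The glossary in section 2 also defines the prophylaxis categories, expressly for analysis. There the entry is "episodic prophylaxis (≤12 weeks"), intermittent is more than 12 and up to 46 weeks, and continuous is more than 46 weeks.

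**The concern.** Two rules in the same sentence and list of 9.7.3.1 appear to exclude each other. A course short enough to be episodic is too short to satisfy the minimum, and a course long enough to satisfy the minimum is no longer episodic. If so, one of the four named prophylaxis settings of the primary endpoint cannot be reported as written. That matters because the primary objective is to describe effectiveness across a variety of clinical settings, and section 7.1 gives efficacy under the different prophylactic regimens used in practice as a reason for the study.

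The cut-points are a smaller, separate matter. Two definitions of the same strata stand in one document, so two programmers could place the same course differently.

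**Working it through.** There is no sample-size, power or error-rate figure to reproduce; for a descriptive study section 9.5 states that "the sample size for the study is not based on statistical considerations". The check is a conversion of units and a comparison of ranges.

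**Inputs**
- Minimum period: 90 days (9.7.3.1), counted on regimen (9.7.1.2).
- Episodic: under 12 weeks (9.7.3.1), or up to and including 12 weeks (glossary).
- Intermittent: from 12 weeks (9.7.3.1), or above 12 weeks (glossary), to 46 weeks in both.
- Continuous: from 46 weeks (9.7.3.1), or above 46 weeks (glossary).

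**Conversion**
- 12 weeks × 7 = 84 days
- 46 weeks × 7 = 322 days
- 90 days ÷ 7 = 12.86 weeks

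**Can a single episodic course reach 90 days?**

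| Definition | Longest episodic course | Shortfall to 90 days | Course lengths that qualify |
|---|---|---|---|
| 9.7.3.1 (<12 weeks) | 83 days | 90 − 83 = 7 | none |
| Glossary (≤12 weeks) | 84 days | 90 − 84 = 6 | none |

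A course that reaches day 90 is at 12.86 weeks and is intermittent under either definition.

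**What else the minimum removes.** Intermittent courses of 84 to 89 days under 9.7.3.1, or 85 to 89 days under the glossary.

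**Could repeated courses qualify?** Only if days are added across courses. The number needed is 90 divided by the course length, rounded up. As illustrations, two courses of 83 days, two of 45 days or four of 28 days would be enough. Two courses of 45 days total 90 days, or 12.86 weeks, so a rule for adding courses would also have to say that the stratum follows the length of each course and not the total.

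**Cut-points side by side**

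| Course length | Glossary | 9.7.3.1 |
|---|---|---|
| Exactly 84 days (12 weeks) | episodic | intermittent |
| Exactly 322 days (46 weeks) | intermittent | intermittent and continuous |

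The 46-week overlap takes the upper limit of the intermittent range as inclusive, which is the ordinary reading. The glossary set does not overlap.

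**The case against.** The strongest objection is that the protocol never says the 90 days must come from one uninterrupted course. The ABR is calculated per subject, 9.7.1.2 speaks of subjects, and each subject is followed for four years, so someone with repeated episodic courses could accumulate 90 days. It can be added that rules for joining courses are often left to the SAP. This stands in part. A reader might infer that the stratum is empty by construction; the text supports only that it is empty unless courses are added. The finding is not that a detail is missing, however. The protocol fixes a category and a minimum that no single course can satisfy together, with no exception and no rule for adding courses.

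A reader might also infer that the reported prophylaxis ABR describes only those who persisted for 90 days. The documents do not say so. The main by-regimen sentence in 9.7.3.1 carries no 90-day condition; the condition belongs to the separate analyses in the next sentence. Section 9.7.1.2 says how the ABR is estimated for subjects who reach 90 days but not four years, and it does not state that all others are excluded.

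Nor does it follow that subjects who stop early contribute nothing. The monthly bleeding rate (MBR) in 9.1.1 and 9.3.1.1 has no stated minimum period, effectiveness is rated at the end of each prophylaxis period, and the infusion and dose tables in 9.7.3.2 have no 90-day rule. The loss is confined to the ABR.

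A further defence is that the 90 days might mean total follow-up. The words on regimen in 9.7.1.2, the denominator in 9.7.1.1 and the prophylaxis clock that starts at the first prophylactic infusion all point the other way.

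Finally, any minimum-observation rule loses some short courses, so the loss of 84 to 89 days is a consequence and not a contradiction. The cut-point conflict touches only courses of exactly 12 or exactly 46 weeks. Both points are fair, and neither adds to the severity.

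**Conclusion.** The conflict is real and follows from the protocol's own figures. Every single episodic course falls at least 7 days short of the minimum under 9.7.3.1, or at least 6 days under the glossary. The episodic ABR stratum is therefore empty unless courses are added within a subject, and nothing in the protocol provides for that. This rests on counting the 90 days on regimen, as 9.7.1.2 states, and per course. Intermittent courses of 84 to 89 days also fall out of the ABR. How many subjects or courses are affected cannot be derived from the document.

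The glossary and 9.7.3.1 also disagree at exactly 12 weeks, and 9.7.3.1 overlaps with itself at exactly 46 weeks.

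This should be fixed, but it does not threaten the study. One stratum of an untested, descriptive analysis is involved, and the overall on-demand and prophylaxis ABRs remain computable.

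**What to change.** 1. Keep the 90-day minimum for individual ABRs in the other strata and state that the episodic stratum is exempt.
2. Report the episodic stratum as the MBR already defined in 9.1.1 and 9.3.1.1, or as total bleeds divided by total days on regimen over all episodic courses, with a 95% confidence interval that allows for several courses from one subject. The total-days rate is the steadier of the two, because it weights each course by its length. Section 9.7.3 already foresees 95% intervals for selected estimates; since 9.5 says that no interval estimation will be applied, the two statements should be aligned when the interval is named.
3. State that the stratum follows the length of each course, so that adding days does not move a subject to another stratum.
4. Use one non-overlapping set of cut-points in both places, for example the glossary's.

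A regression model for every stratum is not needed in a descriptive study of about 55 subjects.

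The cost is a few lines of protocol text and one extra rate table, with no new data collection. The drawback is imprecision. One bleed adds 365.25 ÷ 83 = 4.4 to the ABR of an 83-day course and 365.25 ÷ 28 = 13.0 to that of a 28-day course (an illustrative length). The MBR only rescales this (30.44 ÷ 28 = 1.09 per bleed), so the number of courses, the total days and the interval should be shown beside the rate.

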## 9.7.3.2 Methods of Analysis for Other Primary Efficacy Criteria

The annualized rate of bleeding episodes in joints, target joints, and other anatomical locations for on-demand and prophylaxis subjects will be summarized.

The frequency distribution for number of infusions for bleed treatment will be reported for each of the treatment regimens. The median number of infusions per bleeding episode for each subject will be calculated. The weight-adjusted dose (U/kg) per bleeding episode per subject will be described for on-demand and prophylaxis treatment regimens.

## For treatment of bleeding episodes:

Corresponding to all treated (with FEIBA NF) bleeding episodes the following parameters and statistics will be computed separately by each treatment regimen (prophylaxis, on-demand):

Parameter	Statistics
Total number of subjects infused	Sum
Total exposure days	Median(Q1,Q3)
Total number of infusions	Median(Q1,Q3)
Number of unique lots used	Sum
Units administered per subject, per infusion (U)	Median(Q1,Q3)
Units administered per subject, per week (U)	Median(Q1,Q3)
Units administered per subject, per month (U)	Median(Q1,Q3)
Annualized units administered, per subject (U)	Median(Q1,Q3)
Total units administered, per subject (U)	Median(Q1,Q3)
Weight-adjusted dose per subject, per infusion (U/kg)	Median(Q1,Q3)
Weight-adjusted dose per subject, per week (U/kg)	Median(Q1,Q3)
Weight-adjusted dose per subject, per month (U/kg)	Median(Q1,Q3)
Annualized weight-adjusted dose, per subject (U/kg)	Median(Q1,Q3)
Total weight-adjusted dose, per subject (U/kg)	Median(Q1,Q3)

Total number (%) of treated bleeds and their corresponding hemostatic efficacy ratings using an "excellent-to-poor" 4-point Likert scale by the subjects or caregiver for treatments given at home or by the investigator for treatments given in the hospital/clinic.

## For prevention of bleeding episodes:

Corresponding to subjects given prophylaxis infusions or on demand regimen (FEIBA NF) in this study, the following parameters and statistics will be computed by treatment regimen (prophylaxis, on-demand):

Parameter	Statistics
Total number of subjects infused	Sum
Total exposure days	Median(Q1,Q3)
Total number of infusions	Median(Q1,Q3)
Number of unique lots used	Sum
Units administered per subject, per infusion (U)	Median(Q1,Q3)
Units administered per subject, per week (U)	Median(Q1,Q3)
Units administered per subject, per month (U)	Median(Q1,Q3)
Annualized units administered, per subject (U)	Median(Q1,Q3)
Total units administered, per subject (U)	Median(Q1,Q3)
Weight-adjusted dose per subject, per infusion (U/kg)	Median(Q1,Q3)
Weight-adjusted dose per subject, per week (U/kg)	Median(Q1,Q3)
Weight-adjusted dose per subject, per month (U/kg)	Median(Q1,Q3)
Annualized weight-adjusted dose, per subject (U/kg)	Median(Q1,Q3)
Total weight-adjusted dose, per subject (U/kg)	Median(Q1,Q3)

Efficacy will be assessed by a "excellent-to-poor" 4-point Likert scale by the subjects or care-giver at the end of each prophylaxis period (possibly rated within 24 hours from the end of the prophylactic treatment) or on an annual basis depending on which occurs first. The occurrence of new target joints and bleeding episodes used to detect new target joints will be summarized by treatment regimen

## 9.7.3.3 Secondary Endpoints

The methods of analysis for the secondary efficacy endpoints (see Section 9.1.2.1) are, if available:

- Physical exam using only the pain, bleeding, and physical exam parameters of the Gilbert scale will be summarized for timepoints 0 (screening visit), 1, 2, 3, and 4 (termination visit) years after study start.
- MRI scoring will be summarized for timepoints 0 (baseline), 1, 2, 3 and 4 years after study start (if available).

- X-ray by Pettersson score will be summarized for timepoints 0, 1, 2, 3 and 4 years after study start (if available).
- HJHS will be summarized for timepoints 0, 1, 2, 3 and 4 years after study start (if available).
- Number of invasive surgical procedures, such as (but not exclusively orthopedic) surgery, radiosynovectomy, and chemosynovectomy per year per subject

## 9.7.3.4 Methods of Analysis for Safety Endpoints

The analysis of AEs will be descriptive. All AEs will be categorized according to MedDRA dictionary and summarized by system organ class and preferred term. AEs for which the investigator does not state the relationship to FEIBA NF administration will be included. All AEs will be cross-tabulated for relatedness, seriousness, and severity.

## 9.7.3.5 Methods of Analysis for Health Related Quality of Life (HRQoL) Endpoints

HRQoL assessments, chronic pain scales, daily activity level will be summarized by treatment regimen (on-demand, prophylaxis). If available, changes from baseline to follow-up study visit will be summarized by treatment regimen. Below is list of HRQoL assessment, if available:

- SF-12v2, and EQ-5D questionnaires for adult subjects
  - ➤ The SF-12v2 measures generic health-related quality of life for adults.
  - ➤ The EQ-5D measures health utility in adult subjects.
- SF-10, and EQ-5D-Y questionnaires for pediatric subjects
  - ➤ The SF-10 measures generic health-related quality of life for children aged 4-13 years and is parent-completed.
  - ➤ EQ-5D-Y (Youth version). Descriptive system of youth HRQoL states consisting of five dimensions in subjects aged 7-17 years and can be parent-completed
- Chronic pain associated with hemophilia, defined as "Continuous and/or intermittent pain, related to the pathophysiology of haemophilia, requiring intervention (pharmacological or non-pharmacological pain treatment), in which the cause of pain cannot be readily removed, occurring more than once a week and lasting 3 months or more") 41 and acute pain associated with bleeding episodes will be assessed by

- Numeric Rating Scale (NRS): the NRS measures pain intensity in adults. The most commonly iteration used is the 11-item NRS and its common format is a horizontal bar or line and it is anchored by describing pain severity extremes.
- ➤ Wong Baker Face Scale in pediatric subjects
- Daily activity level will be assessed by
  - ➤ Haemophilia Activity Level scale (HAL) in adults
  - Pediatric Haemophilia Activity Level scale (PedHAL) in children aged 8-17 years

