# 9.2.3 Subject Selection Criteria

Subjects must have been prescribed FEIBA NF for the treatment or prevention of bleeding events by a treating physician prior to the decision to enroll in the study.

No additional diagnostic or monitoring procedures may be applied to subjects, except those that are part of normal/routine clinical practice.

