#### 9.2.3.1 Inclusion Criteria

Subjects of any age who meet **ALL** of the following criteria are eligible for this study and who are willing and able to comply with the requirements of the protocol:

- Subject is a male congenital haemophilia A or B patient with high-responding inhibitor of any titer diagnosed before study entry
- Subject has been prescribed treatment with FEIBA NF as part of routine clinical practice, either on-demand, as prophylactic treatment or during ITI

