## 9.7.3.6 Methods of Analysis for Health Resource Used Related (HRUR) Endpoints

All HRUR parameters will be summarized by treatment regimen (on-demand, prophylaxis). If available, changes from baseline to each follow-up study visit will summarized by treatment regimen. Below is list of all HRUR parameters:

- Health resource use: number of visits at the site
- Unscheduled visits at the site
- Number of hospitalizations related to haemophilia (surgery excluded)
- Length of stay in hospital per stay
- Antiphlogistic drug use
- Infusion log for FEIBA NF
- Acute pain associated with haemophilia, as measured with individual bleeding episodes, using the NRS or the Wong Baker Face Scale in pediatric subjects
- Chronic pain will be assessed on annual basis or more frequently based on current standard at the centre at the screening visit, on each annual visit and at the termination visit by using the NRS or the Wong Baker Face Scale in pediatric subjects
- Number of days lost from school or work due to bleeding episodes or their treatment
- Concomitant medications /Non-drug therapies
- Duration of infusion of FEIBA NF (reconstitution time excluded)

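### Change from baseline by regimen pools subjects already on the regimen with subjects starting it, so it cannot be read as change with the regimen; adding a split by prior exposure is a cheap improvement.

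*Protocol*

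**What the plan says.** **Entry.** Protocol section 9.2.3 states: "Subjects must have been prescribed FEIBA NF for the treatment or prevention of bleeding events by a treating physician prior to the decision to enroll". The matching inclusion criterion in section 9.2.3.1 reads: "Subject has been prescribed treatment with FEIBA NF as part of routine clinical practice, either on-demand, as prophylactic treatment or during ITI". Neither section limits the time since first infusion, requires new use or asks for a washout.

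**Baseline.** Section 9.7.3.3 labels year 0 as the screening visit; the Gilbert components "will be summarized for timepoints 0 (screening visit), 1, 2, 3, and 4 (termination visit) years after study start". Section 9.3.2.1 hands out the HRQoL questionnaires at screening and yearly after that. No baseline is tied to the start of treatment.

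**Change from baseline.** For HRQoL, chronic pain and daily activity, section 9.7.3.5 says: "If available, changes from baseline to follow-up study visit will be summarized by treatment regimen". For resource use, section 9.7.3.6 says: "If available, changes from baseline to each follow-up study visit will summarized by treatment regimen". The regimens named are on-demand and prophylaxis.

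**Safety.** Section 11.1 records adverse events from enrolment onward. Section 9.7.3.4 says: "All AEs will be cross-tabulated for relatedness, seriousness, and severity". Time since treatment start is not a factor in that tabulation. Sections 9.1.2.4 and 9.3.5 also plan a description of SAEs in the on-demand and prophylaxis subgroups.

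**Treatment history.** Table 1 and section 9.3.5.1 collect haemophilia treatment history at screening. The protocol does not use it to divide any analysis. The limitations in section 9.9 mention only how much data will become available.

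**The concern.** Two kinds of subject share one line of the change table. One has been on prophylaxis for years when the screening questionnaire is filled in, so any early gain is already in that score. The other starts prophylaxis at enrolment and is measured before any gain. An average over both depends on how many of each were recruited as well as on what happened to them, and the reader cannot separate the two.

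This matters because section 7.1 sets aims that turn on when a regimen began: joint outcomes when prophylaxis starts early, whether tailored regimen changes improve outcomes, which patients gain most from prophylaxis, and whether safety differs between on-demand and prophylactic use. A pooled table invites reading as evidence on those questions.

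On safety, observation that opens at enrolment cannot contain events from an established user's first exposure. If the share of established users differs between the regimens, the on-demand and prophylaxis SAE descriptions also differ in how much early exposure they cover.

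**Working it through.** The protocol has no figure to reproduce here. The study size of about 55 was chosen for feasibility (section 9.5). The check is an identity, evaluated over a range.

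**Inputs**
- n = 55 evaluable subjects (section 9.5); 4 years of follow-up each (section 9.2.2).
- f = share already on the regimen at enrolment: not given; assumed 0.25 to 0.90.
- D_new = mean change in starters: not given; used as the unit.
- D_est = mean change in established users: not given; assumed from +0.2 to −0.5 times D_new.

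**Step 1. Pooled change**

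Pooled change = (1 − f)·D_new + f·D_est. As a multiple of D_new:

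| f | D_est = 0 | D_est = +0.2·D_new | D_est = −0.2·D_new | D_est = −0.5·D_new |
|---|---|---|---|---|
| 0.25 | 0.75 | 0.80 | 0.70 | 0.63 |
| 0.50 | 0.50 | 0.60 | 0.40 | 0.25 |
| 0.75 | 0.25 | 0.40 | 0.10 | −0.13 |
| 0.90 | 0.10 | 0.28 | −0.08 | −0.35 |

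Example: f = 0.75 and D_est = −0.5·D_new give 0.25 − 0.375 = −0.125.

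The pooled change is zero when D_est = −[(1 − f)/f]·D_new. At f = 0.50 established users would have to lose as much as starters gain; at f = 0.75 a loss of one third of that gain is enough (0.25/0.75).

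**Step 2. What 55 subjects say about early treatment**

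Only starters contribute early-treatment experience: n_new = 55·(1 − f), rounded. With no events, the exact one-sided 95% upper bound on early risk is 1 − 0.05^(1/n_new). With an assumed early risk of 5% per starter, the chance of seeing at least one event is 1 − 0.95^n_new.

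| f | n_new | Upper bound, no events | Chance of ≥ 1 event at 5% risk |
|---|---|---|---|
| 0 | 55 | 5.3% | 94% |
| 0.25 | 41 | 7.0% | 88% |
| 0.50 | 28 | 10.1% | 76% |
| 0.75 | 14 | 19.3% | 51% |
| 0.90 | 5 | 45.1% | 23% |

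A table with a denominator of 55 and no early events would suggest the first row whichever row applies.

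**Step 3. On-demand and prophylaxis side by side**

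Suppose the early risk is 5% for starters in both regimens, but f is 0.25 in one and 0.75 in the other. The expected share of subjects with an early event is then 0.75 × 5% = 3.75% against 0.25 × 5% = 1.25%. The threefold difference comes only from the mix. The two values of f are illustrations.

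**Step 4. The primary endpoint**

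ABR is the number of bleeds in the observed period divided by its days, times 365.25 (section 9.7.1.1). For prophylaxis, "the period for the prophylaxis arm will commence at the first prophylactic infusion once enrolled". It is a rate within the period, with no baseline subtracted, so step 1 does not apply to it.

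**The case against.** The strongest reply is that the study is uncontrolled, descriptive and meant to show routine practice. For that purpose, change over four years in everyone treated, long-term users included, is a legitimate quantity, and a prior-prescription rule is natural in a non-interventional design. This stands: the pooled tables should stay. But a descriptive table still needs a baseline that means one thing, and section 7.1 asks questions that the pooled change cannot answer.

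A second reply is that a subgroup split belongs in the statistical analysis plan, which is not at hand and may contain one. That is partly right. The protocol is not silent, however: it fixes the division as by regimen, and its limitations section leaves prior exposure out.

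Several stronger readings are tempting, and the documents do not support them:
- *Established users change by about zero by construction.* An on-treatment baseline does not fix later change. Section 7.1 describes progressive joint disease and expects regimen changes, so these subjects may improve or decline.
- *A known fraction of the true change is lost.* Every percentage in step 1 rests on assumed f and D_est.
- *The safety data describe mainly patients who already tolerated the product.* The criterion is prescription, not exposure; patients about to start are eligible, and the mix is unknown. Excluding known hypersensitivity does not change that.
- *Early harm is known to be higher.* Section 7.2 reports thrombotic events per infusion (about 4 per 100,000), with known risk factors in 81% of those patients. It does not describe an early-exposure hazard.

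The last objection is cell size. Voluntary, age-specific questionnaires in about 55 subjects already leave few values per cell, and basing every statement on starters alone could discard most of the data. That is a good reason to add the split and not to replace the pooled result.

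**Conclusion.** The point holds in a limited form. As written, change from baseline by regimen in HRQoL, chronic pain, daily activity and resource use mixes on-treatment and pre-treatment baselines in unknown proportion, and cannot be read as change with the regimen. If established users are stable it shows 75%, 50%, 25% or 10% of the starters' change at f = 0.25, 0.50, 0.75 or 0.90; if they decline it can fall below zero. These sizes are conditional on assumptions, since the protocol gives no f, D_new or D_est.

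For adverse events, early-treatment experience is missing to the extent that established users are enrolled, and the on-demand and prophylaxis SAE descriptions can differ through mix alone if that extent differs between regimens. A reader might infer that the primary ABR or a stated figure is wrong; neither follows. No number in the protocol is in error on this point. It is a cheap improvement to the analysis and to the stated limitations.

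**What to change.** 1. From the screening treatment history, classify each regimen period as started on study or ongoing at enrolment. Classify periods rather than subjects, because a long-term on-demand user may begin prophylaxis during follow-up. Confirm that the CRF captures the start date of the current regimen; section 9.3.5.1 does not clearly ask for it.
2. Keep the pooled tables in sections 9.7.3.5 and 9.7.3.6, and add change from baseline by this split.
3. Add SAE and thromboembolic incidence by the same split, within on-demand and prophylaxis.
4. State that the pooled change is not to be interpreted as the effect of starting a regimen.
5. Name prior exposure as a limitation in section 9.9.

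The cost is one derived variable, a check of the CRF, extra table columns and a few sentences. The drawback is small cells with about 55 subjects, so the split results should be presented with their counts and as description only.
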